14. EXPOSURE

14.1. STUDY MEDICATION

Exposure to study medication in days will be presented for the safety population by treatment group.

Summaries of exposure will be based on the first and last study medication administration dates, rather than the blister card information. The first and last study medication administration dates will be taken from the eCRF drug administration and accountability form. Return of the blister card at any given visit is not a prerequisite for inclusion in exposure summary statistics if corresponding dose start and end dates are reported.

The mean daily dose (overall) will be summarized for the safety population by treatment group stratified for all subjects and completers. Completers are defined as follows:

- Week 28: All subjects who completed Week 28. For Japanese subjects Week 28 cut-off will be applied.
- Week 52 (Japan only): All Japanese subjects who completed Week 52.

The modal daily dose (overall and between visits) will likewise be summarized based on the overall study medication exposure. In addition, the number and percentage of subjects receiving the maximum doses of 20 mg, 40 mg, 60mg, 80 mg, 100 mg and 120 mg will be summarized by visits.

The number and percentage of subjects will be summarized for the following exposure duration categories:

- ≥ 1 day, 7, 14, 28, 56, 84, 112, 140, 168, 196, 224, 252, 280, 308, 336, and 364 respectively

Document: K:\DSP\SM-13496\RVA97109\Biostatistics\Documentation\SAP
Author: [REDACTED] Version Number: 1.0
Version Date: 20MAR2018

Template No: CS_TP_BS016 – Revision 3 Reference: CS_WI_BS005
Effective Date: 01May2012

Copyright © 2012 [REDACTED] All rights reserved.
The contents of this document are confidential and proprietary to [REDACTED]. Unauthorized use, disclosure or reproduction is strictly prohibited.

- 1-6, 7-13, 14-27, 28-55, 56-83, 84-111, 112-139, 140-167, 168-195, ..., and 336-364 days

Shift in dose level (SM-13496 20mg, 40mg, 60mg, 80mg, 100mg, 120mg) from the previous scheduled visit to the current scheduled visits will be summarized by each visit.

Return of the blister card at any given visit is not a prerequisite for inclusion in mean daily dose, modal daily dose calculations or dose change summary statistics, if corresponding first and last study medication administration dates are reported.

Exposure to study medication will be presented for all subjects up to Week 28 and repeated for all Japanese subjects up to Week 52 separately. Dose change from previous visit and compliance will be presented for all subjects overall.

14.2. SERUM LITHIUM AND VPA

Observed and changes from LT baseline in serum concentration of lithium (mmol/L) and of VPA (mg/L) will be summarized at each visit, and Week 28 (LOCF) and Week 52 (LOCF) endpoints (subjects within Japan). As an aid to interpretation of serum levels, a summary of exposure to each drug will be provided, and will include the following: prior total daily dose at screening (mmol/L for lithium and mg/L for VPA), total daily dose at LT baseline and each visit, and changes from LT baseline up through Week 28 (LOCF) endpoint and Week 52 (LOCF) endpoint. The analyses above will be conducted using the safety population.

For the purpose of summarizing exposure to lithium, different formulations of lithium are assumed to be equivalent.

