because these drugs are prohibited in the prior study. On the other hand, for patients who did not participate in the prior study, concomitant use of either lithium or VPA will be mandatory in order to evaluate the long-term efficacy and safety of SM-13496 adjunctive to a mood stabilizer.

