5.3 Concomitant medications and therapies

The following information of all medication administered between Visit 0 and follow-up visit will be recorded in the eCRF:

- drug name
- drug type; antipsychotics, antidepressants, mood stabilizers, anxiolytics, hypnotics, antiparkinson drugs, or other
- daily dose (for antipsychotics and mood stabilizers only)
- route of administration
- start date
- stop date
- frequency (for antipsychotics and mood stabilizers only)
- indication

Table 5 shows the restriction on concomitant medications/therapies.

Table 5 Restriction on concomitant medications/therapies

	Screening Phase	Treatment Phase	Follow-up visit
CYP3A4 inhibitors and inducers	A	A	C
Clozapine	A	A	C
Fluoxetine, olanzapine and fluoxetine combination	A	A	C
Depot antipsychotics	A	A	C
Psychotropics (except for mood stabilizers, antiparkinson drugs, anxiolytics, and hypnotics)	B	A	C
MAO inhibitors	A	A	C
Other investigational drugs and post-marketing clinical study medication	A	A	A
Chinese herbal medication	A	A	C
Ginkgo Biloba extract, Kava Kava, St. John's Wort	A	A	C
Electroconvulsive therapy	A	A	C
Mood stabilizers	B	B	C
Medications for extrapyramidal symptoms	B	B	C
Anxiolytics	B	B	C
Hypnotics	B	B	C
Medications for complications	B	B	C

A, Prohibited; B, Restricted; C, No restrictions

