5.3.2 Restricted concomitant medications/therapies

5.3.2.1 Psychotropic medications

(1) Psychotropics (except for mood stabilizers, antiparkinson drugs, anxiolytics, and hypnotics)

Psychotropics excluding mood stabilizers, antiparkinson drugs, anxiolytics, and hypnotics (see Items (2) to (5) in this section) will be restricted as follows:

- For patients untreated with psychotropic medications at screening, psychotropic medications will be prohibited from screening until the end of the treatment phase.
- For patients treated with any psychotropic medication at screening, the psychotropic medications should be titrated down appropriately and terminated before the initiation of the study treatment. Psychotropic medications will be prohibited during the treatment phase.

(2) Mood stabilizers

For patients who completed the prior study

Mood stabilizers (excluding lithium and VPA) will be prohibited from the initiation of the study treatment until the end of the study treatment. Either lithium or VPA can be used.

For patients who did not participate in the prior study

Mood stabilizers (excluding lithium and VPA) will be prohibited from the initiation of the study treatment until the end of the study treatment. Either lithium or VPA will be administered adjunctively from the initiation of the study treatment until the end of the study treatment.

Guidance on the dose of lithium and VPA

The dose of lithium and VPA will be in principle within the range approved in each participating country. The dose of lithium and VPA can be modified based on patient condition and serum concentrations that will be obtained at each study visit. If necessary, the investigator can use either lithium or VPA at a lower or higher dose than approved with prior consultation with the medical monitor. If any safety concerns are raised, treatment with either lithium or VPA should be terminated.

Guidance on switching between lithium and VPA

Switching between lithium and VPA will be not recommended, but may be permitted on a case-by-case basis following a consultation with the medical monitor.

(3) Medication for extrapyramidal symptoms (eg, antiparkinson drugs)

Medications for extrapyramidal symptoms (eg, antiparkinson drugs) will be restricted as follows from screening to the end of the study treatment:

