5.5 Contraception

Women of childbearing potential can be enrolled. However, adequate contraception should be used throughout the study and for at least 30 days after receiving the last dose of the study drug to avoid the patient or his partner becoming pregnant.

Adequate contraception is defined as continuous use of either a 2-barrier method (eg, condoms and spermicide, diaphragms and spermicide), a hormonal contraceptive, or abstinence.

Acceptable hormonal contraceptives include the following: (a) contraceptive implant (such as Norplant[®]), implanted at least 90 days prior to baseline; (b) injectable contraception (such as medroxyprogesterone acetate injection) given at least 14 days before baseline; (c) oral contraceptive taken as directed for at least 30 days before baseline.

Patients who are of non-reproductive potential, ie, patient who is surgically sterile, has undergone tubal ligation, or is postmenopausal (defined as at least 12 month of spontaneous amenorrhea or between 6 and 12 months of spontaneous amenorrhea with follicle stimulating hormone concentrations within postmenopausal range as determined by laboratory analysis) are not required to remain abstinent or use adequate contraception.

If a female patient has been confirmed being pregnant, the patient should immediately discontinue the study medication. If a pregnancy has been confirmed in a female patient or a female partner of patient, the investigator should follow the procedure outlined in Section 7.2 (see Page 64).

6. Measurements

Study schedule is shown in Table 1, Table 2 and Table 3 (see Pages 27 to 32). The following data will be collected. For completers of the prior study, assessments at Week 6 in the prior study will be used for baseline in the present study, which means any procedures (eg, assessments, measurements, sampling) will not be performed at Visit 1 actually.

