6.3.7 Blood concentration of lithium or valproate

From patients receiving lithium or VPA, the amount of blood specified in Table 9 or 10 will be collected to obtain 0.5 mL of serum at all scheduled visits (including at screening) and at discontinuation during the period when a patient is receiving either lithium or VPA. Blood concentration of lithium or valproate will be measured at the central laboratory.

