6.2. BASELINE

For subjects who completed the prior double-blind study, the double-blind baseline (DB baseline) is defined as the last non-missing assessment (including unscheduled assessments) collected on or prior to the reference start date of the prior double-blind study (D1002001). In the case where the last non-missing assessment and the reference start date coincide, that assessment will be considered pre-baseline, but AEs and medications commencing on the reference start date will be considered post-baseline. The long-term baseline (LT baseline) is defined as Week 6 of the prior double-blind study (D1002001).

For subjects who did not participate in the prior double-blind study, DB baseline is not defined, and LT baseline is defined as the last non-missing assessment (including unscheduled assessments) collected on or prior to the reference start date of the long-term study (D1002002). In the case where the last non-missing assessment and the reference start date coincide, that assessment will be considered pre-baseline, but AEs and medications commencing on the reference start date will be considered post-baseline.

Post-baseline data will be defined as non-missing data on or after Day 1 and through 7 days after the final administration of study medication in the treatment phase (excluding baseline).

In the event that data recorded in the prior double-blind study (D1002001) would actually be collected after the reference start date of the long-term study (D1002002), this data will be included in this long-term study in looking for maximum on treatment values, but will not be taken into account for any other summaries.

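### SAP 14.2 gives a lithium/VPA daily dose in serum-concentration units and carries on-drug serum levels forward after the drug is stopped

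*SAP*

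**What the plan says.** SAP 14.2 plans two linked summaries in the safety population. The first is serum level: "serum concentration of lithium (mmol/L) and of VPA (mg/L) will be summarized at each visit", with change from LT baseline and with Week 28 (LOCF) and, in Japan, Week 52 (LOCF) endpoints. The second is exposure to each drug, offered as help in reading the levels: "prior total daily dose at screening (mmol/L for lithium and mg/L for VPA), total daily dose at LT baseline and each visit", again with change from LT baseline through the LOCF endpoints.

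Five other rules bear on this.

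- **Baseline.** SAP 6.2 sets LT baseline for completers at Week 6 of the prior study. For new recruits it is the last non-missing value up to the first dose in this study.
- **Prior study.** Protocol 3.3 says lithium/VPA is not mandatory for completers "because these drugs are prohibited in the prior study". In the present study Protocol 5.3.2.1 makes it optional for them: "Either lithium or VPA can be used".
- **Sampling.** Protocol 6.3.7 restricts collection to times "during the period when a patient is receiving either lithium or VPA". For completers, the opening of Protocol section 6 says "any procedures (eg, assessments, measurements, sampling) will not be performed at Visit 1 actually".
- **Stopping and switching.** Protocol 5.3.2.1 provides for terminating lithium or VPA on safety concerns. It allows switching case by case after consulting the medical monitor.
- **LOCF.** SAP 6.3.1 carries forward the last non-missing post-baseline value up to 7 days after the last dose of study medication. For Japanese subjects who go on past Week 28, the Week 28 visit itself serves as the Week 28 endpoint.

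**The concern.** A daily dose cannot be expressed in mmol/L or mg/L. Followed literally, the instruction either repeats the serum level or labels a dose as a concentration, which defeats the purpose of a table meant to help interpret levels. SAP 14.3 gives mg/day derivations for study medication only, so nothing else in the SAP settles the lithium/VPA unit.

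The LOCF rule is a separate problem. Its only time limit is tied to study medication. A level measured on lithium therefore stays eligible as the endpoint long after lithium was stopped, provided the subject remains on study drug.

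At stake is the description of background treatment. New recruits take lithium or VPA by design, and efficacy and safety results are split by mood stabilizer. SAP section 18 repeats a lithium/VPA exposure summary for Japanese subjects, so an uncorrected specification would feed those tables too.

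**Working it through.** **1. Units.** SAP 14.2 gives serum concentration in mmol/L (lithium) and mg/L (VPA). The next sentence gives the screening daily dose in the same two units. Dose at LT baseline and at visits has no unit. A usable source exists: Protocol 5.3 records the daily dose of mood stabilizers in the eCRF.

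**2. Which subjects can have an LT-baseline level.** Protocol Tables 9 and 10 count the blood draws, so I first reproduced their totals as volume × number of samples (mL).

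- Outside Japan: 2×4 + 11.5×4 + 3.5×5 = 8 + 46 + 17.5 = 71.5 (female); + 10×4 = 111.5 (male).
- Japan, completers: 2×7 + 11.5×7 + 3.5×8 = 14 + 80.5 + 28 = 122.5; + 10×7 = 192.5.
- Japan, new recruits: 2×9 + 13×1 + 11.5×8 + 3.5×8 = 18 + 13 + 92 + 28 = 151; + 10×9 = 241.

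All six totals match. Draws usable for lithium/VPA are the chemistry draws plus the lithium/VPA-only draws:

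- Outside Japan: 4 + 5 = 9, which is Visits 2 to 10.
- Japan, completers: 7 + 8 = 15, which is Visits 2 to 16.
- Japan, new recruits: 1 + 8 + 8 = 17, which is Visits 0 to 16.

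No completer has a planned baseline draw. A new recruit has one only if already on the drug, and Protocol 4.1.2 admits recruits who are not. (I rely on these counts because the baseline column of Protocol Table 1 is not reliably legible in the text available to me.)

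**3. How many changes in level are missing.** Let f be the fraction of the 325 planned completers who start lithium/VPA. The documents do not give f. The number without a baseline level is 325 × f:

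- f = 10%: 32.5, about 33, or 8% of the 405 planned subjects (325 + 80).
- f = 30%: 97.5, about 98, or 24%.
- f = 50%: 162.5, about 163, or 40%.

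These completers outnumber the 80 new recruits once f exceeds 80/325 = 24.6%. They exceed half of all subjects only if f exceeds (0.5 × 405)/325 = 62.3%. New recruits not on the drug at baseline add to the count; their number is not stated.

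**4. Where LOCF carries an off-drug level.** Setting SAP 6.3.1 against Protocol 6.3.7:

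- Outside Japan, Week 28 (LOCF): the gap applies. A subject whose last lithium sample is at Week 8 and who completes Week 28 is reported with a level 28 − 8 = 20 weeks old.
- Japan, leaving before Week 28: the gap applies.
- Japan, continuing past Week 28: no gap at Week 28, because that visit's own value is used.
- Japan, Week 52 (LOCF): the gap applies. A last level at Week 28 would be 52 − 28 = 24 weeks old in a subject who completes Week 52.

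A subject who moves from lithium to VPA keeps the old lithium level and gains a VPA level, and so is counted at the endpoint under both. SAP 3.6 adds a category for subjects on both drugs because the data collected require it. It does not say whether these subjects overlapped or switched.

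**The case against.** The wrong unit sits in one parenthesis, on the screening dose. The variable is called a total daily dose, the eCRF collects it, and the table shells, which are not available here, may already show the right unit. For dose, a completer's Week 6 value is naturally 0 because the drugs were prohibited. New recruits must take lithium or VPA throughout, switching is discouraged, and the Week 28 exception protects every Japanese subject who continues. Observed levels by visit appear alongside, and new recruits have their own column (NR-LUR). The study has no hypothesis, and no efficacy or safety result is stated to come from this table.

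Most of this stands, and it limits the size of the point. It does not remove it. The written unit is wrong, the SAP does not say whether an untaken drug counts as 0 or as missing, and the LOCF rule as written reports off-drug subjects at on-drug levels.

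Four stronger readings are tempting, and the documents do not support them.

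- A reader might infer that the table is wrong for most subjects, or for the 325/405 = 80% who are completers. Lithium/VPA is optional for them: those who never take it contribute no level, and those who start have a missing change while their observed levels remain valid.
- A reader might infer that no dose would be shown. The bad unit is attached only to the screening dose.
- A reader might take this as the only planned exposure table. SAP section 18 plans another.
- A reader might infer that endpoint exposure is materially overstated. The number who stop or switch while staying on study drug is not given.

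**Conclusion.** The point holds as a minor correction to a descriptive exposure table. The dose unit is wrong as written. The LOCF rule for serum levels gives a misleading endpoint for subjects who stop or switch lithium/VPA while remaining on study drug, in the three settings in step 4 where the gap applies. How many subjects that involves cannot be derived from the documents.

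The baseline issue is one of missing values, and it concerns serum level; for dose the SAP lacks only a stated rule. The range of 33 to 163 completers rests on the planned 325 and on my assumption that 10% to 50% of them start lithium or VPA.

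**What to change.** Amend SAP 14.2 and carry the changes through to the lithium/VPA exposure tables in section 18.

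- **(a) Dose.** Report total daily dose in mg/day from the eCRF at screening, LT baseline and each visit. Count 0 mg/day when the drug is not taken, so that change from LT baseline is defined. Show the number receiving the drug beside it, so that zeros are not read as low doses. Protocol 5.3 does not state the unit in which dose is entered; I assume it can be expressed in mg.
- **(b) Level.** Summarise observed levels by visit among subjects receiving that drug at the visit, with n. Limit change from LT baseline to subjects with a measured LT-baseline level.
- **(c) LOCF.** Limit the LOCF endpoint for serum levels to subjects still receiving that drug at the endpoint.

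The cost is SAP wording and table shells; dose and start and stop dates are already collected. The downside is a smaller n at the LOCF endpoint for levels. No dosing or clinical rule changes.

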14.3. DERIVATIONS

Cumulative dose (mg) = Sum of all the doses the subject is expected to take during the study.

Duration of exposure (days) = (date of last study medication administration – date of first study medication administration) + 1.

Interruptions, compliance, and dose changes are not taken into account for duration of exposure.

Mean daily dose (mg/day) of study medication = Cumulative dose (mg)/Duration of exposure (days).

The modal daily dose (mg/day) is defined as the daily dose that is taken for the most time for each study phase, in terms of number of days among all doses taken. If there are ties, therefore more than one modal daily dose for a subject, the last modal dose administered will be used in the summaries.

The modal daily dose (mg/day) between visits is calculated similarly to the modal daily dose for overall. Therefore, the dose that is taken for the most time from the visit date to the day prior to the next visit date.

15. STUDY MEDICATION COMPLIANCE

Compliance will be presented for the safety population by treatment group, both continuously (mean percentage) and categorically (compliant versus non-compliant, non-compliant <75% and non-compliant >125%, and subjects with any missing compliance).

Document: K:\DSP\SM-13496\RVA97109\Biostatistics\Documentation\SAP
Author: [REDACTED] Version Number: 1.0
Version Date: 20MAR2018

Template No: CS_TP_BS016 – Revision 3 Reference: CS_WI_BS005
Effective Date: 01May2012

Copyright © 2012 [REDACTED] All rights reserved.
The contents of this document are confidential and proprietary to [REDACTED]. Unauthorized use, disclosure or reproduction is strictly prohibited.

15.1. DERIVATIONS

At each visit, prior to dispensing study medication, previously dispensed study medication will be retrieved and assessed by tablet count. Compliance will be calculated overall as follows:

- Percent compliance = (number of tablets taken / number of tablets should have taken) x 100.
- Number of tablets taken = number of tablets dispensed – number of tablets returned. Lost tablets are considered to have been returned for the purpose of calculating compliance.
- Number of tablets should have taken = (number of tablets supposed to take in a day) x (number of exposure days).

If the number of tablets returned is missing, compliance will be missing. Non-compliance is defined as less than 75% or more than 125% non-missing overall compliance with the study medication. Subjects with missing compliance are not classified as non-compliant, and are not considered to be protocol deviators.

16. EFFICACY OUTCOMES

16.1. EFFICACY

The efficacy analysis will be performed for the safety population by treatment group. Listings will include all enrolled subjects.

16.1.1. EFFICACY VARIABLE & DERIVATION

16.1.1.1. Montgomery-Asberg Depression Rating Scale (MADRS)

The MADRS is a clinician-rated assessment of the subject's level of depression, measured at Screening, Baseline, Week 1 to Week 28 (for subject outside Japan) and Week 1 to Week 52 for subject in Japan.

The measure contains 10 items that measure apparent and reported sadness, inner tension, reduced sleep and appetite, difficulty concentrating, lassitude, inability to feel, and pessimistic and suicidal thoughts. Each item is scored in a range of 0 to 6 points, with higher scores indicating increased depressive symptoms. The MADRS total score is the sum of all 10 items scores and can be obtained from the eCRF directly.

The total score is calculated as the sum of all the component scores of the MADRS scale. The MADRS total score ranges from 0 to 60. Higher scores are associated with greater severity of Bipolar I disorder.

16.1.1.2. Young Mania Rating Scale (YMRS)

The YMRS is an 11-item instrument used to assess the severity of mania in subjects with a diagnosis of bipolar disorder, measured at Screening, Baseline, Week 1 to Week 28 for subject outside Japan and Week 1 to Week 52 for subject within Japan.

The 11 items are: Elevated Mood, Increased Motor Activity Energy, Sexual Interest, Sleep, Irritability, Speech (Rate and Amount), Language-Thought Disorder, Content, Disruptive-Aggressive Behavior, Appearance, and Insight. The YMRS is a clinician-rated assessment. Seven items are rated on a 5-point scale, ranging from 0 to 4, and four items are rated on a 9-point scale, ranging from 0 to 8. The YMRS uses operationally-defined anchor

Document:	K:\DSP\SM-13496\RVA97109\Biostatistics\Documentation\SAP	Version Number:	1.0
Author:	[REDACTED]	Version Date:	20MAR2018

Template No: CS_TP_BS016 -- Revision 3
Effective Date: 01May2012

Reference: CS_WI_BS005

Copyright © 2012 [REDACTED] All rights reserved.
The contents of this document are confidential and proprietary to [REDACTED].
reproduction is strictly prohibited.

[REDACTED] Unauthorized use, disclosure or

points and the normal expected score is >20. Ratings are based on subject self-reporting, combined with clinician observation (accorded greater score).

The YMRS total score is the sum of the 11 individual items and ranges from 0 to 60. Higher scores are associated with a greater severity of mania. If one or more items are missing at a visit, the total score will be set to missing.

